3.1. Inclusion Criteria

- 3.1.1. Patients 16 years or older with Philadelphia chromosome (Ph)- or BCR/ABL-positive CML (as determined by cytogenetics, FISH, or PCR).
- 3.1.2. Patients must have received FDA-approved TKI therapy for at least 18 months and not have increased their dose of FDA-approved TKI in the last 6 months. Patients participating on frontline protocols 2005-0048 (nilotinib) and 2005-0422 (dasatinib) are eligible for enrollment on this study.
- 3.1.3. Phase II patients must be in complete cytogenetic remission.
 - 3.1.3.1. For the phase I portion of the study, patients may be included without a complete cytogenetic remission provided they are in chronic phase
- 3.1.4. Phase II patients must have detectable BCR-ABL transcript levels meeting at least one of the following criteria:
 - 3.1.4.1. Patient has never achieved a major molecular response, and transcript levels have shown in at least two consecutive measures separated by at least 1 month to have increased by any value, or
 - 3.1.4.2. Achieved a major molecular response that has been lost with an increase in transcript levels by at least 1-log, confirmed in two consecutive analyses separated by at least 1 month, or
 - 3.1.4.3. The patient has received therapy for at least 2 years and does not have a sustained major molecular response, or
 - 3.1.4.4. The patient has received therapy for at least 5 years and does not have a sustained complete molecular response.
 - 3.1.4.5. Patients included in the phase I portion of the study are eligible regardless of their level of BCR-ABL transcripts.

- 3.1.5. Patients must not have had a known continuous interruption of imatinib therapy of greater than 14 days or for a total of 6 weeks in the 6 months prior to enrollment.
- 3.1.6. Patients must sign an informed consent indicating that they are aware of the investigational nature of this study in keeping with the policies of the hospital.
- 3.1.7. ECOG performance status ≤ 2 .
- 3.1.8. Adequate organ function defined as: bilirubin $< 2x$ upper limit of normal (ULN) (unless associated with Gilbert's syndrome), and ALT or AST $\leq 2.5x$ ULN.
- 3.1.9. ANC $\geq 1 \times 10^9/L$ and platelets $\geq 50 \times 10^9/L$.

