5.2. Evaluation During Study

- 5.2.1. Physical exam and evaluation of toxicity (clinic visit or telephone interview):
 - 5.2.1.1. Phase I portion: every 2 weeks for the first month, then every month for the first 3 months, then every 3 months (± 1 month) until month 6, then every 6 to 12 months.
 - 5.2.1.2. Phase 2 portion: every 3 months (± 1 month) until month 6, then every 6 to 12 months.
- 5.2.2. CBC, platelet, differential every 1-2 weeks for 8 weeks, then at the start of every cycle. Differential not required if $WBC \leq 0.5 \times 10^9/L$.
- 5.2.3. Bone marrow aspirate with cytogenetics or FISH every 3-6 months in year 1, then as clinically indicated.
- 5.2.4. Total bilirubin, SGPT or SGOT, and creatinine every 1-2 weeks for 8 weeks, then before each cycle.
- 5.2.5. Quantitative PCR (peripheral blood and/or bone marrow) before each cycle for 3 cycles, then every 3-6 cycles until one year, then every 6-12 cycles.
- 5.2.6. Peripheral blood and bone marrow for correlative studies every 3-6 months in year 1, then every 6-12 months. Methylation studies will also be done on days 5, 10 and 28 (all ± 3 days) of the first cycle. Not all optional samples may be collected. (Optional – Appendix A, B & C).

6. Criteria for Response

- 6.1. A favorable response for the primary endpoint is defined as a greater than a one-log reduction of BCR-ABL transcript levels from the baseline level at the time vaccination was initiated, or a disappearance of BCR-ABL transcripts (i.e., complete molecular response).

7. Criteria for Removal from Study

- 7.1. The patient receives CML-directed therapy other than TKI and AZA.
- 7.2. The patient develops disease progression defined as confirmed loss of CCyR, confirmed loss of CHR or transformation to accelerated or blast phase.
- 7.3. The dose of TKI is increased or new therapies for their leukemia are added.
- 7.4. The patient has a continuous interruption of imatinib therapy for greater than 6 weeks.
- 7.5. The patient withdraws consent.
- 7.6. The treating physician considers it in the best interest of the patient.
- 7.7. Pregnancy or suspected pregnancy

8. Adverse Event Reporting

- 8.1. Adverse event is any untoward medical occurrence that may present during treatment with a pharmaceutical product but which does not necessarily have a causal relationship with this treatment.

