9.2.1.1. Three patients will be enrolled at the starting dose level

9.2.1.2. If 0/3 patient experiences DLT at a given level, enroll three patients to the next higher dose level

9.2.1.3. If 1/3 patient experiences DLT at a given level, enroll additional three patients to the same dose level

9.2.1.4. If 2/3 or 2/6 patients experience DLT at a given level, the MTD has been exceeded and dose escalation will be stopped. Up to three additional patients will be enrolled at the next lower dose level if only 3 patients were treated at that level.

9.2.2. MTD is defined as the highest dose level in which 6 patients have been treated and one or fewer patient experiences DLT.

The MTD identified in phase I part will be recommended for phase II. If MTD is not determined, the highest AZA level of 75 mg/m²/d x 3 days will be used as the recommended phase II dose.

A maximum of 18 patients will be accrued for phase I part. The data from the 6 patients treated at the recommended phase II dose level (MTD or 75 mg/m²/d x 3 days if MTD is not determined) will be used in phase II part.

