9.3. Phase II

The primary endpoint for phase II portion is the decrease of transcript levels by at least one log (or undetectable transcript level) within 12 months. Including the 6 patients treated at the recommended phase II dose level in the phase I part, a total of 36 patients will be accrued.

9.3.1. **Efficacy Monitoring**

Since the efficacy of the drug will be assessed over a long period of time (12 months) and the accrual rate is relatively fast (1-2 patients per month), no formal futility monitoring rule will be applied. However, the PI and the study committee will meet regularly, and the study will be stopped early if consensus has been reached on any clear indications of poor efficacy of the drug.

9.3.2. **Toxicity Monitoring**

The method of Thall, Simon, and Estey will be used to perform interim safety monitoring [1]. The safety monitoring of the trial will be initiated after the first 6 patients have been evaluated, and then monitored continuously. The monitoring rule for toxicity is $P(\theta_E > 0.20 | \text{data}) > 0.90$, where θ_E is the proportion of any DLT (as defined in section 4.3.3), and is assumed to follow a non-informative prior of Beta (0.4, 1.6). Namely, the trial will be terminated if at any time during the study there is a more than 90% chance that the average rate of DLT is more than 20%. The stopping boundaries of the trial are ≥ 3 out of 6, ≥ 4 out of 7, ≥ 5 out of 10, ≥ 6 out of 14, ≥ 7 out of 18, ≥ 8 out of 22, ≥ 9 out of 26, ≥ 10 out of 30, ≥ 11 out of 34 patients experienced DLT.

Table 2: Operating characteristics of Safety Monitoring (based on 10000 simulations)				
True Probability	Stop Probability	Trial Sample Size Percentile		
		25%	50%	75%
0.10	0.02	36	36	36
0.20	0.25	36	36	36
0.30	0.69	6	17	36
0.40	0.96	6	8	16

All calculations were performed using Multc99.

9.4. **Statistical Methods**

Data analysis will be performed using SAS or S-plus, whichever is appropriate. All patients who receive at least one dose of therapy will be included in the primary efficacy and toxicity analysis. Patients who do not have molecular response and

withdraw within 12-months after initiation of treatment will be counted as failure in the primary efficacy analysis.

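### The primary response in section 6.1 is measured from a vaccination this trial does not give, no PCR is named as baseline, and sections 6.1 and 9.3 define response differently

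*Combined protocol and SAP*

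**What the plan says.** Section 6.1 defines a favorable response for the primary endpoint as a fall of more than one log "from the baseline level at the time vaccination was initiated, or a disappearance of BCR-ABL transcripts". Section 9.3 gives the phase II primary endpoint as "the decrease of transcript levels by at least one log (or undetectable transcript level) within 12 months" and mentions no baseline.

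Two provisions could supply a baseline PCR, and neither is called that. Section 5.1.5 asks for a pretreatment quantitative PCR unless one was done in the preceding 3 months. Section 5.2.5 asks for one before each of the first 3 cycles. Section 9.4 suggests a time origin: non-responders who "withdraw within 12-months after initiation of treatment will be counted as failure in the primary efficacy analysis".

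On who is counted, section 3.1.4 states that "Phase II patients must have detectable BCR-ABL transcript levels". Section 3.1.4.5 exempts phase I: "Patients included in the phase I portion of the study are eligible regardless of their level of BCR-ABL transcripts". Section 3.1.3.1 adds that in phase I "patients may be included without a complete cytogenetic remission provided they are in chronic phase". Section 9.2.2 carries some of these patients forward ("The data from the 6 patients treated at the recommended phase II dose level"), and 9.3 counts them in the total of 36. Section 9.4 sets the analysis population: "All patients who receive at least one dose of therapy will be included in the primary efficacy and toxicity analysis".

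**The concern.** This is the only primary efficacy endpoint, and it is tested in a single arm against a fixed 5% null, so no control group would absorb a scoring error. There are three defects.

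- **Reference event.** The event named in 6.1 does not occur in this trial. Putting the start of azacitidine in its place still leaves the sample open. Sections 3.1.4.1 and 3.1.4.2 admit patients because their transcripts are rising, so a value up to 3 months old and a fresh one can differ, and the response threshold is itself one log.
- **Size of fall.** Section 6.1 requires more than one log; 9.3 requires at least one log. This is minor.
- **Transcript clearance.** Section 6.1 speaks of disappearance, which implies that transcripts were there before. Section 9.3 speaks of an undetectable level, which need not imply that. The difference matters only for someone undetectable at entry. Phase II entrants cannot be, but a carried-over phase I patient can.

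Two analysts following the text could therefore choose different baselines, or score the same carried-over patient differently. A response credited to a patient undetectable before treatment would not be an effect of treatment.

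**Working it through.** **Inputs.** From 9.4: null 5%, alternative 20%, one-sided 5% test, n = 36, power 87%, and a statement that the study is positive if a 20% response is reached. From 9.2.2 and 9.3: 6 of the 36 come from phase I. The number k of carried-over patients undetectable at entry is not in the documents; k = 0 to 6 is an assumed range.

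**The plan's own figure.** Exact binomial with n = 36:
- P(X ≥ 4 | 0.05) = 0.104, above 5%.
- P(X ≥ 5 | 0.05) = 0.0324 and P(X ≥ 5 | 0.20) = 0.873.

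The smallest cut-off that keeps the 5% level is 5/36, and its power reproduces the stated 87%. The protocol does not write this cut-off down.

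Read as an observed rate, the 20% rule gives 0.20 × 36 = 7.2, so at least 8 responders: P(X ≥ 8 | 0.05) = 0.0003 and P(X ≥ 8 | 0.20) = 0.434.

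**Effect of crediting k patients.** They count as responders automatically and the other 36 − k respond at 5%. For cut-off c, the false-positive chance is P(Bin(36 − k, 0.05) ≥ c − k).

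| k | c = 8 (20% rule, observed) | c = 5 (implied by 87% power) |
|---|---|---|
| 0 | 0.03% | 3.2% |
| 1 | 0.15% | 9.6% |
| 2 | 0.6% | 24.1% |
| 3 | 2.3% | 49.6% |
| 4 | 7.4% | 80.6% |
| 5 | 20.1% | 100% |
| 6 | 44.6% | 100% |

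**Effect of keeping them in the 36 as non-responders.** Power is P(Bin(36 − k, 0.20) ≥ c).

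| k | c = 5 | c = 8 |
|---|---|---|
| 0 | 87.3% | 43.4% |
| 1 | 85.7% | 40.1% |
| 2 | 83.8% | 36.7% |
| 6 | 74.5% | 23.9% |

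**Effect of excluding them from the denominator.** For every n from 30 to 35 the exact 5% cut-off remains 5, so power at that cut-off is the same as in the c = 5 column above. Under the 20% rule the required count falls with n:
- k = 1: 0.20 × 35 = 7, so 7/35, power 56.7%.
- k = 2: 0.20 × 34 = 6.8, so 7/34, power 53.4%.
- k = 6: 0.20 × 30 = 6, so 6/30, power 57.2%.

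The vaccination wording and the missing baseline do not enter the sample-size calculation. Their effect is on how individual patients are scored, and the documents give no data from which to size it.

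**The case against.** Most of this can be called editorial. Section 6.1 already says baseline, the treatment plan contains only azacitidine and a TKI, and 9.4 counts its 12 months from the start of treatment, so few readers would be misled about the reference event. That stands for the event, but it does not settle which PCR is used.

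The two PCR provisions may not compete. The waiver in 5.1.5 would have little purpose if 5.2.5 always required a fresh PCR before cycle 1. A coherent reading is that 5.1.5 supplies the pretreatment value and 5.2.5 governs later cycles. This also stands: a reader might infer that a fresh pre-cycle-1 sample is certain to exist, and the documents do not establish that. The remedy should not depend on one.

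The crediting reading of 9.3 is not forced. The parenthesis about undetectable transcripts can be taken to qualify the decrease, and a patient undetectable throughout has had none. Sections 1.1.2 and 9.1 describe the intended population as having minimal residual disease, which points the same way. These passages show intent, but they do not override 3.1.4.5 or the all-treated population in 9.4, and 9.3 remains open to both readings.

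Finally, the larger error rates rest on an unwritten cut-off and an unknown k. Under the only success rule the protocol writes, read as an observed rate, four of the six would have to be credited before 5% is exceeded. That is correct and limits the weight of the point.

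**Conclusion.** The endpoint definition is wrong as written and should be corrected. It is anchored to an event outside this trial, it has no designated baseline PCR, and it differs between the two sections that state it. These defects hold whatever the value of k.

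The effect on the error rate is conditional. It requires that a carried-over patient was undetectable at entry, that 9.3 is read to credit that patient, and, for the sizes above, that all others respond at 5%. With k = 0 there is no effect. Because phase I also admits patients without a complete cytogenetic remission, the carried-over group may instead have high transcript levels.

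A reader might infer that the trial's false-positive rate is in fact inflated, or that 9.3 necessarily counts patients undetectable before treatment. The documents support neither. They allow that scoring without requiring it, and they do not say whether any such patient exists.

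**What to change.** Put one identical definition in 6.1 and 9.3. A responder has, within 12 months of the first azacitidine dose, either:
- a fall of at least one log from the last PCR taken before that dose, within the 3-month window of 5.1.5; or
- undetectable transcripts, having been detectable at that same baseline.

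Delete the reference to vaccination. State that a carried-over phase I patient undetectable at baseline stays in the 36, as 9.4 requires for all treated patients, but cannot be a responder.

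This is a change of wording and needs no added sample or visit. The price, if such patients exist, is power: at 5/36 it falls from 87.3% to 85.7% with one, 83.8% with two and 74.5% with six; at 8/36 from 43.4% to 40.1%, 36.7% and 23.9%.

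The alternative is to exclude them from the denominator. That gains nothing at the exact-test cut-off. Under the 20% rule it would give higher power (56.7%, 53.4% and 57.2% for one, two and six), but it would mean changing the analysis population in 9.4. If the sponsor prefers it, that change should be written into 9.4 before the response data are examined.

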1. OBJECTIVES

1.1. Primary Objective:

- 1.1.1. **Phase I:** To determine the DLT and MTD of the combination of azacitidine (AZA) and a tyrosine kinase inhibitor (TKI) in patients with chronic myeloid leukemia (CML).
- 1.1.2. **Phase II:** To determine the clinical activity of the combination of AZA and a TKI in patients with CML in complete cytogenetic remission (CCyR) with minimal residual disease.

1.2. Secondary Objectives:

- 1.2.1. **Phase I**
 - 1.2.1.1. To determine the clinical activity of the combination of AZA and a TKI in patients with CML
- 1.2.2. **Phase II**
 - 1.2.2.1. To determine the safety of the combination of AZA and a TKI in patients with CML in CCyR with minimal residual disease.
- 1.2.3. **Both phases**
 - 1.2.3.1. Determine the effect of therapy over DNA methylation
 - 1.2.3.2. Investigate the correlation of DNA methylation and response to therapy

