4.2.3. Definition of Dose-Limiting Toxicity (DLT)

4.2.3.1. DLT will be defined by events that are clinically significant and possibly related to study drug occurring during the first 4 weeks (1 cycle) of therapy.

4.2.3.2. Non-hematologic DLT is defined as grade 3 or 4 toxicity (NCI common criteria, version 4.0) that is clinically significant and

considered to be at least possibly related to the study drug. Grade 3 or 4 nausea, vomiting and diarrhea will be considered DLT only if not controlled by optimal therapy.

4.2.3.3. Grade 3 biochemical abnormalities (e.g., lipase or bilirubin elevation) will only be considered DLT if accompanied by clinical consequences. Grade 3 or 4 electrolyte abnormalities will only be considered DLT if possibly related to study drug and not corrected by optimal replacement therapy.

4.2.3.4. Hematologic DLT is defined as grade ≥ 3 neutropenia and/or thrombocytopenia with a hypocellular bone marrow lasting for 6 weeks or more after the start of a course. (In case of a normocellular bone marrow, 8 weeks with pancytopenia will be considered DLT). Anemia will not be considered for the definition of DLT.

4.2.4. If dose-level 0 exceeds MTD, subsequent patients will be treated at dose level -1. Additional cohorts at lower doses (down to dose level -4) may be included if higher doses exceed MTD. If dose level -4 exceeds MTD, the study will be terminated.

4.3. **Phase II:** The dose to be used for the phase II portion of the study is $75\text{mg}/\text{m}^2$ daily for 3 days, unless MTD is defined at a lower dose level in the phase I portion of the study in which case that would become the dose to be used for the phase II portion. Other dose levels shown in Table 1 will be used for dose adjustments for toxicity or lack of improvement (as described in section 4.5.5) during therapy. For phase II portion of the study, if at any time patients need to be escalated to dose level +2 or +3, if at any time 33% or more of patients experience DLT at this dose level during the first cycle they receive at this dose, this would be considered to have exceeded MTD and that dose level should not be used any further.

4.4. Treatment with AZA (in both phase I and phase II) may be repeated every 28 days. The start of subsequent cycles may be delayed to allow for recovery of any adverse events to grade 1 or less.

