Adverse drug reaction is a response to a drug which is noxious and unintended and which occurs at doses normally used in man for prophylaxis, diagnosis, or therapy of disease or for the modification of physiologic function.

Assessing causal connections between agents and disease is fundamental to the understanding of adverse drug reactions. In general, a drug may be considered a contributory cause of an adverse event if, had the drug not been administered, 1) the event would not have happened at all, 2) the event would have occurred later than it actually did, or 3) the event would have been less severe.

The Investigator or physician designee is responsible for verifying and providing source documentation for all adverse events and assigning the attribution for each event for all subjects enrolled on the trial.

- 8.2. Adverse Events (AEs) will be evaluated according to the latest CTC version and documented in medical record. Only unexpected AEs will be recorded in the Case Report Form (CRF). Expected events during leukemia therapy are:

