8.2.1. Myelosuppression Related Events (due to disease or leukemia therapy)

- 8.2.1.1. febrile or infection episodes not requiring management in the intensive care unit

8.2.1.2. epistaxis or bleeding except for catastrophic CNS or pulmonary hemorrhage

8.2.1.3. anemia, neutropenia, lymphopenia, thrombocytopenia, leukopenia

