8.2.3.4. Hospitalization for the management of any of the above expected events

8.3. Abnormal hematologic values will not be recorded on the case report form. For abnormal chemical values, the apogee or nadir (whichever is appropriate) will be reported per course on the case report form.

8.4. **Serious Adverse Event Reporting (SAE)**

An adverse event or suspected adverse reaction is considered “serious” if, in the view of either the investigator or the sponsor, it results in any of the following outcomes:

- Death
- A life-threatening adverse drug experience – any adverse experience that places the patient, in the view of the initial reporter, at immediate risk of death from the adverse experience as it occurred. It does not include an adverse experience that, had it occurred in a more severe form, might have caused death.
- Inpatient hospitalization or prolongation of existing hospitalization
- A persistent or significant incapacity or substantial disruption of the ability to conduct normal life functions.
- A congenital anomaly/birth defect.

Important medical events that may not result in death, be life-threatening, or require hospitalization may be considered a serious adverse drug experience when, based upon appropriate medical judgment, they may jeopardize the patient or subject and may require medical or surgical intervention to prevent one of the outcomes listed in this definition. Examples of such medical events include allergic bronchospasm requiring intensive treatment in an emergency room or at home, blood dyscrasias or convulsions that do not result in inpatient hospitalization, or the development of drug dependency or drug abuse (21 CFR 312.32).

- Important medical events as defined above, may also be considered serious adverse events. Any important medical event can and should be reported as an SAE if deemed appropriate by the Principal Investigator or the IND Sponsor, IND Office.
- All events occurring during the conduct of a protocol and meeting the definition of a SAE must be reported to the IRB in accordance with the timeframes and procedures outlined in “The University of Texas M. D. Anderson Cancer Center Institutional Review Board Policy for Investigators on Reporting Unanticipated Adverse Events for Drugs and Devices”. Unless stated otherwise in the protocol, all SAEs, expected or unexpected, must be reported to the IND Office, regardless of attribution (within 5 working days of knowledge of the event).

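### Expected AEs and all abnormal blood counts are kept off the CRF and no DLT record is specified, so a CRF-based safety analysis would be incomplete and haematologic DLT could not be verified from it

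*Combined protocol and SAP*

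**What the plan says.** **What is recorded.** Section 8.2 has AEs graded and documented in the medical record, then limits the CRF: "Only unexpected AEs will be recorded in the Case Report Form (CRF"). The list of expected events that follows includes:

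- "anemia, neutropenia, lymphopenia, thrombocytopenia, leukopenia" (8.2.1.3);
- "febrile or infection episodes not requiring management in the intensive care unit" (8.2.1.1);
- bleeding other than catastrophic CNS or pulmonary haemorrhage (8.2.1.2);
- fatigue, electrolyte, chemistry and coagulation abnormalities, and abnormal haematologic values (8.2.2);
- "Hospitalization for the management of any of the above expected events" (8.2.3.4).

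Section 8.3 adds: "Abnormal hematologic values will not be recorded on the case report form". The next sentence of 8.3 does put the extreme of each abnormal chemistry value on the CRF for every course.

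**What has to be measured.** Phase II has a secondary objective (1.2.2.1): "To determine the safety of the combination of AZA and a TKI in patients with CML in CCyR with minimal residual disease". DLT is the phase I primary endpoint (9.2) and the event counted by the phase II stopping rule (9.3.2). It also decides, under 4.3, whether dose levels +2 and +3 stay in use. Section 4.2.3.4 says: "Hematologic DLT is defined as grade ≥ 3 neutropenia and/or thrombocytopenia with a hypocellular bone marrow lasting for 6 weeks or more". The duration is counted from the day a course begins, and a separate 8-week pancytopenia criterion applies if the marrow is normocellular. Section 9.4 includes every patient given at least one dose in the toxicity analysis.

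**The concern.** The recording rule and the safety aims do not fit together. Cytopenia is the subject of the haematologic DLT definition, yet it is kept off the CRF twice: as an expected event in 8.2 and as a laboratory value in 8.3. Some non-haematologic events are affected too. A clinically significant, possibly related grade 3 or 4 infection outside intensive care, bleed or episode of fatigue can be a DLT under 4.2.3.2, but it is expected and so is not entered as an AE.

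Two things are at stake. A safety summary drawn from the CRF would leave out common, non-serious clinical toxicity and all cytopenias. And the DLT counts behind dose escalation and early stopping would have no CRF data against which a monitor or later analyst could check them.

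**Working it through.** **1. Where each kind of safety information goes**

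| Information | On the CRF? | Other route |
|---|---|---|
| Unexpected AEs | Yes (8.2) | Medical record |
| Expected clinical AEs, not serious | No (8.2) | Medical record only |
| Expected AEs that are serious | No (8.2) | IND Office, electronic SAE system (8.4) |
| Chemistry extremes per course | Yes (8.3) | Medical record |
| Neutrophil and platelet values | No (8.3) | Medical record; counts every 1-2 weeks for 8 weeks, then at each cycle start (5.2.2) |
| DLT determination | Not specified | Investigator judgement from source |

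**2. Can haematologic DLT be derived from the CRF?** Section 4.2.3.4 needs the grade of neutropenia or thrombocytopenia, its duration (6 or 8 weeks) and marrow cellularity. Grade and duration come from counts that 8.3 excludes, and no CRF item for cellularity is described. The derivation is therefore not possible from the CRF as specified.

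**3. The plan's own figures.** The stopping rule in 9.3.2 uses a Beta(0.4, 1.6) prior. After r DLTs in n patients the posterior is Beta(0.4 + r, 1.6 + n − r), and the trial stops if P(rate > 0.20 | data) > 0.90.

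- n = 6, r = 2: Beta(2.4, 5.6) gives 0.707, continue.
- n = 6, r = 3: Beta(3.4, 4.6) gives 0.914, stop.
- n = 7, r = 3: Beta(3.4, 5.6) gives 0.873, continue; r = 4: Beta(4.4, 4.6) gives 0.970, stop.

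Repeating this for n = 6 to 36 reproduces all nine stated boundaries. An exact binomial recursion, checking after each patient from 6 to 36, gives the stop probabilities:

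| True DLT rate | Table 2 | Exact |
|---|---|---|
| 0.10 | 0.02 | 0.025 |
| 0.20 | 0.25 | 0.256 |
| 0.30 | 0.69 | 0.707 |
| 0.40 | 0.96 | 0.954 |

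All agree to within 2 percentage points. Nothing in 9.3.2 needs to change.

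**4. What those figures assume.** Table 2 assumes that every DLT is counted. If only a share f were counted, the rule would act on a rate of f × p. The documents give no value for f; the values below are assumptions, shown as a range.

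| Share counted, f | p = 0.30: f × p | Stop probability | p = 0.40: f × p | Stop probability |
|---|---|---|---|---|
| 1.00 | 0.300 | 0.71 | 0.40 | 0.95 |
| 0.75 | 0.225 | 0.36 | 0.30 | 0.71 |
| 0.50 | 0.150 | 0.10 | 0.20 | 0.26 |
| 0.25 | 0.075 | 0.01 | 0.10 | 0.02 |

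This shows how sensitive the rule is to incomplete counting. It does not forecast under-counting in this trial.

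**The case against.** The case on the other side is substantial. All AEs are graded, attributed and source-documented (8.1, 8.2), and blood counts are frequent early on. Section 9 does not say that DLTs are counted from CRF pages, and in a 3+3 design with continuous monitoring the investigators can judge DLT from the chart as it happens. All SAEs, expected or not, go to the IND Office, so an expected event leading to inpatient admission is captured there. Chemistry extremes are on the CRF. Section 10.2 requires study data to be entered in the institution's data system, which could hold a DLT field.

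These points stand, and they rule out several stronger readings that a reader might infer:

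- *Safety cannot be analysed, or the stopping rules lack data.* Not supported: the information exists at source and part of it is captured centrally.
- *Every expected category would show 0 of 36.* Not supported: electrolyte and other chemistry extremes would appear as laboratory values, and serious events in the SAE system.
- *Most of these events would be caused by the combination, because the patients are in remission.* The documents give no basis for this. Phase I patients need not be in complete cytogenetic remission (3.1.3.1). Patients may also enter with neutrophils of 1 and platelets of 50 × 10⁹/L (3.1.9), so some cytopenia may predate azacitidine.

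What the objection does not do is return cytopenias or non-serious expected clinical events to the CRF. The general instruction in 10.2 names no count or DLT field, and 8.3 excludes the counts outright. A prolonged cytopenia without admission need not be an SAE.

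**Conclusion.** The point holds in a limited form. It rests on an explicit recording rule rather than on detail left unstated. An analysis based on the CRF as specified would omit non-serious expected clinical AEs and all cytopenias, so objective 1.2.2.1 and the 9.4 toxicity analysis would be met only in part. Haematologic DLT could not be derived or verified from the CRF, although it can be identified from the medical record.

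The number of events lost cannot be stated, because the documents give no toxicity rate for this combination. The boundaries and Table 2 are sound, provided that DLT counting is complete. The conclusion assumes that the safety report is drawn from the CRF and that no DLT or count form exists beyond what the protocol describes. If such a form exists, the protocol should say so and the concern narrows accordingly. The change should be made, but it does not call the design into question.

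**What to change.** Amend 8.2 and 8.3 so that the CRF records, whether the event is expected or not:

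1. all AEs of grade 3 or higher, and all AEs at least possibly related to azacitidine or the TKI, with grade, attribution, and start and stop dates;
2. neutropenia and thrombocytopenia of grade 3 or higher with start and recovery dates, and marrow cellularity wherever a marrow is done, because 4.2.3.4 cannot be applied without it;
3. a yes/no DLT determination for each patient.

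Leave the SAE reporting rules in 8.4 as they are; they already ignore expectedness.

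Two references should be reconciled in the same amendment. Sections 9.2 and 9.3.2 point to 4.3.3 for the DLT definition, which is in 4.2.3. Section 8.2 grades by the latest CTC version, while 4.2.3.2 and 4.5.2 name version 4.

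The cost is modest extra data entry for up to 48 patients, from counts, marrow reports and AE notes already collected. Treatment, sample size and stopping boundaries are unaffected.
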